#### 4.2. Inclusion Criteria

Individuals who meet all of the following criteria are eligible for enrollment as study participants. Participants in this trial will have participated in our separate (IRB protocol #12656 or 19512) screening protocol performed at day -28. Results obtained from the screening protocol will be used to initially determine eligibility as described below.

All subjects:

1. Subjects must be able to understand and provide written informed consent.
2. Age 18 to  $\leq 40$  years of age, any gender, any racial/ethnic origin
3. Female subjects of childbearing potential must have a negative pregnancy test upon study entry (day -7) and before each procedure involving pharmacologic interventions (days 0, 4, and 7).
4. Female (and male) subjects with reproductive potential, must agree to use FDA approved methods of birth control for the duration of the study such as, but not limited to, birth control pills, contraceptive foam, diaphragm, IUD, abstinence, or condoms.
5. Participants must be willing to comply with study procedures and requirements.
6. Negative test for serum neutralizing antibody to RV16 at enrollment visit ( $<1:8$ ) (Visit 1).
7. Negative CoVID-19 test within 72 hrs of RV inoculation
8. Afebrile and negative CoVID screening questions on day of RV inoculation

Allergic Rhinitis Subjects:

1. Allergy as determined by  $\geq 1$  positive prick skin test (wheal  $\geq 5$  mm diameter and 3mm larger than the diluent control) to Virginia inhalant panel within 5 years (done as part of screening protocol), and a history of symptoms of sneezing, rhinorrhea, pruritus, nasal congestion, and/or allergic conjunctivitis on natural exposure to relevant allergens.
2. Negative methacholine challenge (less than 20% decline in FEV1 at  $\leq 8$ mg/ml) within 1 year
3. FEV1  $\geq 70\%$  predicted or FEV1/FVC  $\geq 80\%$ .
4. No history of wheezing with viral infection in the last 6 years, and no use of rescue inhalers or long-term controllers for asthma in the last 6 years.

Allergic Asthmatic Subjects:

1. Allergy as determined by  $\geq 1$  positive prick skin test (wheal  $\geq 5$  mm diameter and 3mm larger than the diluent control) to Virginia inhalant panel with 5 years (done as part of screening protocol). Subjects are not required to have allergy symptoms at the time of study. Subjects will report history of symptoms of sneezing, rhinorrhea, pruritus, nasal congestion, and/or allergic conjunctivitis on natural exposure to relevant allergens.
2. Asthma determined by physician diagnosis and by a positive methacholine challenge (at least 20% fall in FEV1 at a methacholine concentration of  $\leq 16$  mg/ml) at screening protocol visit before enrollment (obtained within the past year).
3. Asthma must be controlled as determined by ACT score  $\geq 20$  at Visit 1 and normal lung function (FEV1  $\geq 80\%$  predicted and FEV1/FVC ratio  $>0.65$ ).

#### 4.3. Exclusion Criteria (all subjects)

Individuals who meet any of these criteria are not eligible for enrollment as study participants:

1. Positive test for serum neutralizing antibody to RV16 at enrollment visit ( $\geq 1:8$ )(Visit 1).

2. Upper airway modified Jackson criteria symptom scores  $\geq 7$  at time of inoculation.
3. Chronic heart disease including bradycardia, lung diseases other than asthma, or other chronic illnesses including epilepsy, peptic ulcer disease, thyroid disease, urinary tract obstruction, vagotonia, autoimmune disease, primary or secondary immunodeficiency or any household contacts who are known to be immune deficient. Any medical conditions that could be adversely affected by the administration of cholinergic agent.
4. Any use of nasal corticosteroids, LT modifiers, omalizumab, within 4 weeks prior to Visit 1.
5. Current use of  $\beta$ -blockers or cholinesterase inhibitors (for myasthenia gravis)
6.  $\beta 2$ -agonist use  $\geq 4$  days/week in any week or  $\geq 2$  nights during the month before Visit 1.
7. Recent (within 3-yr) asthma exacerbation requiring urgent care visit (unless the treatment involved only the use of a bronchodilator), hospitalization, or oral CCS
8. Intubation or management in the ICU for an asthma exacerbation ever.
9. An upper or lower respiratory tract infection within 2 months prior to enrollment.
10. Previous nasal or sinus surgery within the last 12 months
11.  $>5$  pack-year smoking history or any smoking within the past 6 mos.
12. Hemoglobin  $<11.5$  g/dL for non-African American subjects or hemoglobin  $< 11.0$  g/dL for African American subjects detected at Visit 1.
13. Laboratory values (other than hemoglobin and ANC) measured at Visit 1 that are considered to be of clinical relevance by the Investigator.
14. Absolute neutrophil count (ANC)  $<1500$  cells/mm^3 (or 1.5 K/ $\mu$ L) or absolute lymphocyte count (ALC)  $<800$  cells/mm^3 detected at Visit 1.
15. Use of investigational drugs within 12 weeks of participation
16. Past or current medical problems or findings from physical examination or laboratory testing that are not listed above, which, in the opinion of the investigator, may pose additional risks from participation in the study, may interfere with the participant's ability to comply with study requirements or that may impact the quality or interpretation of the data obtained from the study.

#### 4.4. Selection of Clinical Sites/Labs

N/A

## 5. Known and Potential Risks and Benefits to Participants

### 5.1. Risks of Investigational Product or Intervention

Approximately 2000 volunteers have been challenged in studies conducted by [name], [name], [name], [name], and their colleagues over the last 30 years and no serious complications attributable to the viral infection have been detected. The clinical syndrome associated with experimental infection is well described. Challenge of volunteers with approximately 300 TCID50 of RV produces infection in 90 to 95% of susceptible volunteers. Symptoms first appear within 24 hours after inoculation and peak at 48-72 hours after challenge. The clinical syndrome is comparable to that reported in natural colds (52, 53). Approximately one-third of RV infections, whether natural or experimental, are asymptomatic. Virus shedding in infected volunteers follows a pattern similar to that of the symptoms. Virus concentrations in nasal lavage fluid, based on titers in culture, generally peak 2-3 days after challenge and then rapidly decrease. Virus can be recovered by culture in 20% of subjects on day 18 after challenge, but no virus shedding is detected by day 20 (55). To the best of our knowledge, human RV-16 has not been withdrawn from investigation or marketing in any country for any reason related to safety or effectiveness. In our studies, we have observed neutropenia in most of the 29 asthmatic subjects and also 16 controls following inoculation with RV-16 in our experimental challenges, which we believe is in keeping with the recruitment of neutrophils into the airways stimulated

by RV. However, except for the possibility of bronchitis, which occurs infrequently in experimental infections, no subject has developed clinically significant bacterial infections in our studies, including bacterial sinusitis. Additionally, no subject in our studies with RV-16 has developed ANC's less than 1000 cells/mm^3. Should any subject develop an ANC or ALC below 500/ $\mu$ L on Day 4, a repeat CBC will be done on Day 14 to ensure that the value has returned to baseline or into the normal range, whichever is lower. If the value has not recovered at on Day 14, another CBC will be completed on Day 21. If the value remains low following the Day 21 draw, the subject will be referred to his or her regular healthcare provider for follow-up.

The results from experimental challenges in asthmatics with RV-16 and RV-39 at the University of Virginia indicate that RV challenges can be done safely in mild asthmatics who are not using anti-inflammatory medications. This has also been the experience of others using the RV challenge model elsewhere. In addition, RV challenges have also been performed on mild/moderate persistent asthmatics who are very well controlled on long-term controllers (inhaled corticosteroids with or without long-acting  $\beta$ -agonists) without untoward reactions.(58) In our first study of asthmatics enrolled in challenge studies at the University of Virginia using RV-39, one of 19 subjects needed intervention with inhaled steroids during peak cold symptoms (47). One college student enrolled in our studies needed a short course of oral steroids when challenged with RV-39 produced under GMP conditions. This student was one out of 23 asthmatic subjects who were inoculated with this pool in our experimental challenges. Additionally, 3 of the last 12 asthmatic subjects challenged with this pool of RV-39 more recently used albuterol more frequently for chest symptoms during peak symptoms, but they experienced no significant declines in their FEV1 values monitored at home or observed in our clinical research center. No subject enrolled in any of our studies who have been challenged with either RV-16 or -39, or in studies published by others using RV-16 that we are aware of, has experienced an exacerbation requiring hospitalization or treatment in the ER. In our previous published study with RV-16 prior to the virus being manufactured under GMP conditions, 13 of the 16 subjects with mild asthma reported mild symptoms of cough, wheeze, or chest discomfort during the infection, but none required intervention with anti-inflammatory medications such as inhaled or oral corticosteroids (1). We are interested to use this new pool because the majority of published data from experimental challenges with RV have been done using RV-16, which is helpful in comparing our results (e.g., (8, 31)).

All subjects in the proposed study will be inoculated with RV-16 and monitored daily for 4 days following inoculation in the clinical research center at UVA hospital and again on day 7 dpi. Daily monitoring will include upper and lower respiratory symptoms scores, and FEV1 measurements (using a hand held FEV1 monitor given to each subject), which will be recorded twice daily (morning and evening) on diary cards. Subjects will also be recording the number of puffs of albuterol used daily from metered dose inhalers. In addition, monitoring each morning will include a physical examination focused on the respiratory tract, along with spirometry and measurements of expired nitric oxide (FeNO). This monitoring will be done to enhance our ability to detect changes during the acute infection and to ensure safety. The research team member will be a licensed physician or nurse and will be readily available should any problems occur. Thus far, no significant problems or serious adverse events have occurred for any of the asthmatics inoculated with either RV-16 or RV-39. The inclusion of mild-/moderate-persistent asthmatics who are very well controlled on inhaled CCS could lead to more severe exacerbations. However, this has not been the experience of other research groups enrolling this population (58). Furthermore, as noted, the average American has 4 respiratory infections/yr and we would argue that as none of these subjects will have had even a modest asthma exacerbation in the previous 3 years (over which time they will on average have had 12 RV infections) we do not feel this modification adds an untoward risk to the study. And that the current safety monitoring criteria will continue to suffice.

As for any adverse long-term safety effects of an experimental RV-16 infection, the cold symptoms observed have been generally similar to, but a bit shorter in duration than a natural RV infection (see above). Because most adults will

experience at least one or two viral induced colds a year, it would be very difficult to differentiate any adverse effects of an RV-16 experimental infection from the effects of a subsequent natural respiratory tract infection in an effort to evaluate any safety problems long-term.

## **5.2. Risks of Investigational Product or Intervention cited in Medical Literature**

Recently, in European studies, challenges with RV-16 were well-tolerated by subjects with moderately severe asthma who were treated with inhaled corticosteroids (9, 59) . However, asthmatic subjects in those studies were using inhaled steroids at the time of inoculation, which would interfere with our goals of judging the effects of RV infection on lower respiratory tract symptoms and bio-markers of inflammation.

## **5.3. Risks of Other Protocol Specified Medications**

Albuterol: Risks of albuterol used to treat RV-induced symptoms or to reverse symptoms induced by methacholine and less likely spirometry/FeNO include palpitations and tremor.

Oral corticosteroids: Short courses of oral CCS (3-5 days) may be indicated to treat more serious asthma exacerbations. Short-term administration of prednisone is associated with appetite stimulation, weight gain, hyperglycemia, transient increases in blood pressure, fluid retention, stomach upset, and agitation/insomnia.

Nasal decongestant/nasal analgesic. Subjects will have a nasal decongestant (oxymetazoline) and analgesic (lidocaine 4%) sprayed into their nose prior to the nasal biopsy. Oxymetazoline will also be given to subjects with directions for use if needed following the procedure to treat mild delayed bleeding. In addition, biopsy sites may be injected with additional lidocaine (1%) and epinephrine (1:100,000). There are no side effects to topical application of oxymetazoline. Lidocaine at very high doses can produce cardiac arrhythmias, however, there is no risk for this occurring at the doses that will be used for this study.

## **5.4. Risks of Study Procedures**

Nasal lavage: may be associated with some discomfort due to <10 second breath hold and the feeling of fluid in the nares. A potential complication is acute bacterial sinusitis (sinus infection) although this has never occurred in thousands of procedures done by us.

Light nasal scraping: An additional nasal specimen will be obtained by using an ASI Rhino-Pro® nasal mucosal curette plastic device to do a light scraping along the inferior turbinate of each nostril to collect epithelial cells. The nasal scrapings will produce local discomfort. It is possible that nasal scraping may cause temporary epistaxis, which would be treated with local pressure for several minutes.

Nasal lining fluid: An additional nasal specimen will be obtained by applying a small piece (1 X 1 cm) of sterile gauze to inferior turbinate for 4 to 5 minutes in each nostril to collect a sample of epithelial cell lining fluid (about 0.2 ml). Other than local discomfort no complications are known to occur with this procedure.

Blood draw: Drawing blood causes transient discomfort and may cause fainting. Ecchymosis (bruising) at the blood draw site may occur but can be prevented or lessened by applying pressure to the draw site for several minutes. The use of sterile technique will make infection extremely unlikely.

Lung function tests, exhaled nitric oxide testing, and methacholine challenge: The risk of lung function tests and eNO testing is the discomfort of exhaling forcefully. This may be associated with mild shortness of breath, cough, chest tightness, wheezing, or chest soreness. Most patients do not have any symptoms. Symptoms (if they occur) are mild, last only a few minutes, and disappear following the inhalation of a bronchodilator medication, which will be

administered as needed. The methacholine challenge will more likely produce mild shortness of breath, cough, chest tightness, and wheezing. These effects will last only a few minutes and will disappear following the inhalation of a bronchodilator.

Nasal biopsy. Risks of nasal biopsy include local discomfort and bleeding. Since the biopsies will be performed under direct visualization hemostasis can be readily achieved with application of pressure, topical oxymetazoline or application of silver nitrate cautery. Vasovagal events are expected in a small number of subjects; therefore, subjects will be closely monitored for such symptoms during the biopsy procedure. If signs of a vasovagal episode are present, the chair will put in a reclining position until the subject no longer reports symptoms or demonstrates signs consistent with low blood pressure. There is a theoretical risk of infection although in our experience this has never occurred. To assess the degree of post-procedure signs and symptoms the first 5 number subjects will not undergo the biopsy until the completion of the nasal biopsy in the prior participant.

Silver Nitrate Cautery: Lidocaine will have been applied prior to the cauterization; however, once the anesthetic wears off, subjects may experience tenderness and discomfort for a few days as well as a runny nose for up to a week after the treatment. Silver nitrate cautery also carries a rare risk of infection.

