### 3. Study Design

#### 3.1. Description of Study Design

A total of 60 subjects will be enrolled in this open label challenge study over a period of 48-54 months (September 2016 – March 2021). These will include 20 subjects in each of 3 cohorts: healthy controls, allergic rhinitis controls, and asthmatics. At Visit 1 subjects will have baseline assessments of lung function and blood work. Viral inoculation will be performed on day 0 and assessments of cold and allergy symptoms, nasal viral titers, nasal mediators, lung function, and FeNO will be obtained on days 0 and days 1, 2, 3, 4, and 7 post-infection (dpi). In addition, methacholine challenges (days -7 and 4) will be performed. Finally, nasal biopsies will be performed on day 4 to assess extent of viral infection and nature of cell death (apoptosis v. necrosis). Each subject will complete the study at day 14.

Table I: Study Outline\*\*\*

Visit #:	1	2	3	4	5	6	7	8	9
	Day -7	Day 0	Day 1	Day 2	Day 3	Day 4	Day 7	Day 14**	Day 21
Symptom Assessment	X	X	X	X	X	X	X	X	X
Negative CoVID19 screen (afebrile/preserved sense of smell)	X	X	X	X	X	X	X	X	X
Pregnancy Test	X	X				X	X		
Viral antibody serology/CBC	X								
Virus inoculation		X							
Viral titers		X	X	X	X	X	X		
FEV1/ FeNO	X	X	X	X	X	X	X	X	
Nasal Scraping		X	X	X	X	X	X		
Nasal Washes / Sponge		X	X	X	X	X	X		
Nasal Biopsy						X			
Blood for Th immune deviation / AEC	X					X			
Methacholine Challenge	X					X			

\*\*\* If subject is still symptomatic at day 14 they will be contacted at day 21 with the possibility of an unscheduled visit. A Day 21 in-person visit will be scheduled if ANC or ALC falls below 500/ $\mu$ L, and does not return to baseline following the Day 14 blood draw. If disease activity increases after day 7 or other concerns arise either between visits 6 and 7 or after visit 8, participants will be instructed to contact study personnel and may be asked to return to the study site for an "unscheduled" visit.

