### **Between Visits 6 and 7 (Days 5 and 6)**

Subjects will complete the diary card daily

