### **8.3. Unscheduled Visits**

If disease activity increases after day 7 or other concerns arise either between visits 6 and 7 or after visit 8, participants will be instructed to contact study personnel and may be asked to return to the study site for an “unscheduled” visit. Unscheduled visits will include a physical exam, interim medical history, recording of adverse events and medications, and spirometry testing. Diary cards will also be collected as applicable.

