### **8.4. Visit Windows**

Study visits should take place within the time limits specified below. Visit 1 screening/baseline visit will take place between 5 days and 28 days prior to scheduled inoculation. Post-inoculation visits will only take place on the specific day with the exception of visit 7, which will be permitted to have a  $\pm$ 24 hr window, and visit 8, which will have a +5 day window.

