### 11.5. Study Stopping Rules

The enrollment and dosing of RV-16 in the study may be suspended pending review by the NIAID DSMB and the University of Virginia IRB for the following reasons:

- Any subject has a severe asthma exacerbation that requires treatment in the emergency room or hospitalization
- $\geq 2$  subjects experience severe asthma exacerbations requiring oral corticosteroids for  $\geq 5$  days, pending further expedited review.
- Any subject treated for pneumonia
- Any subject dies until expedited review is completed to determine whether the death might have resulted from any of the study procedures.
- Complications post biopsy requiring an urgent care visit in  $\geq 2$  subjects.
- Any death that occurs in the study, which is possibly or definitely related to study treatment regimen.
- The occurrence of a Grade 3 or higher related SAE in 2 or more of the study participants who have received a study treatment.

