**Study mandated procedures:**

- Spirometry / exhaled breath nitric oxide (FeNO) – Wheezing or bronchoconstriction requiring treatment with bronchodilators within 30 minutes from the procedure, Coughing requiring treatment with bronchodilators within 30 minutes from the procedure
- Methacholine challenge - Wheezing or bronchoconstriction requiring treatment with bronchodilators within 30 minutes from the procedure, Coughing requiring treatment with bronchodilators within 30 minutes from the procedure
- Nasal scrapings – Active epistaxis within 24 hours after the procedure lasting longer than 1 hour
- Nasal wash / sponge – Acute sinusitis diagnosed by a study clinician or based upon assessment of outside health records within 72 hours after the procedure
- Nasal biopsy - Active epistaxis within 24 hours after the procedure lasting longer than 1 hour, or infection needing medical treatment. Vasovagal symptoms and/or vasovagal syncope that do not respond to lowering of the participant's head
- Phlebotomy - Fainting/vasovagal event; Bruising at puncture site larger than 2 cm diameter, Bleeding from puncture site lasting longer than 5 minutes, Swelling at puncture site larger than 2 cm

Events not related to study participation will be recorded on the Adverse Events form if deemed to be Grade 2 or higher in severity.

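### The stagger for the first five nasal biopsies releases the next subject when the prior biopsy ends, so it guarantees no observation afterwards

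*Combined protocol and SAP*

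**What the plan says.** The nasal biopsy paragraph of Section 5.4 (Risks of Study Procedures) gives the stagger a purpose, which is to gauge how marked the signs and symptoms are once the procedure is over. The rule that follows is that "the first 5 number subjects will not undergo the biopsy until the completion of the nasal biopsy in the prior participant". No interval, follow-up contact or review is attached. The only monitoring described in that paragraph is for vasovagal symptoms while the biopsy is being done.

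Other sections that bear on this:

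- **Adverse event definition** (Section 12.2.1, study mandated procedures). For the biopsy, this includes "Active epistaxis within 24 hours after the procedure lasting longer than 1 hour, or infection needing medical treatment".
- **Delayed bleeding** (Section 5.3). Subjects are given oxymetazoline "to treat mild delayed bleeding".
- **Contact after biopsy** (Section 8.2). The biopsy is on Day 4. For Days 5 and 6 the only instruction is "Subjects will complete the diary card daily". The next scheduled visit is Visit 7, on Day 7 ± 24 hours (Section 8.4).
- **Unscheduled contact** (Section 8.3, and the footnote to Table I in Section 3.1). If "other concerns arise either between visits 6 and 7 or after visit 8, participants will be instructed to contact study personnel".
- **Stopping rule** (Section 11.5). "Complications post biopsy requiring an urgent care visit in" at least two subjects may suspend enrollment and dosing.

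**The concern.** The purpose and the trigger do not match. A rule meant to show what happens after a biopsy should release the next subject some time after the last one, and this one releases at the end of the procedure. It would show an event during the biopsy, such as a vasovagal reaction. It need not show a bleed that starts at home that evening, which is the kind of event that the adverse event definition and the take-home decongestant both anticipate.

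Nothing else fills the gap automatically. The biopsy stopping rule needs urgent care visits in two subjects, so it cannot act on a first event. The stagger is therefore the only biopsy-specific rule that holds back the next subject after a single biopsy. If two early biopsies fall within about a day of each other, the second can go ahead before the first subject's 24-hour outcome is known.

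The stakes are small. A subject may decline the biopsy without this counting as a deviation (Section 15.2), the biopsy serves an exploratory outcome (Section 3.3), and the expected-risk table in Section 12.2.3 lists epistaxis as infrequent and easily stopped.

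**Working it through.** The plan gives no figure to reproduce. The check compares sections and then asks how often the gap could matter.

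**Guaranteed observation**

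| Item | Source | Value |
|---|---|---|
| Release of next subject | Section 5.4 | end of prior biopsy |
| Guaranteed wait after that | Section 5.4 | 0 hours |
| Nosebleed adverse event window | Section 12.2.1 | 24 hours |
| Staff-initiated contact on Days 5 and 6 | Section 8.2 | none, diary only |
| Next scheduled visit | Section 8.4 | Day 7 ± 24 hours, about 2 to 4 days after biopsy |

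The guaranteed wait falls 24 hours short of the protocol's own window. The subject can telephone in the meantime, so a bleed may reach staff before Day 7. That route depends on the subject and does not hold the next biopsy.

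**Can early biopsies fall close together?** Day 4 has no visit window: "Post-inoculation visits will only take place on the specific day with the exception of visit 7" (and Visit 8, which also has one). Subjects inoculated on the same day therefore reach biopsy on the same day. The documents neither plan nor forbid same-day inoculation.

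**How often, as an illustration.** The inputs are 60 subjects and an accrual period of 48 to 54 months (Section 3.1) or 5 years, that is 60 months (Synopsis). Assumptions not in the documents: 30.4 days per month, random independent inoculation dates (exponential gaps), and every subject accepting biopsy.

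- Mean gap in days, m = months × 30.4 / 60.
- Chance that one gap is under 1 day = 1 − exp(−1/m).
- Five subjects have four gaps. Chance that at least one is under 1 day = 1 − exp(−4/m).

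| Accrual (months) | m (days) | One gap under 1 day | At least one of four |
|---|---|---|---|
| 48 | 24.3 | 4.0% | 15.2% |
| 54 | 27.4 | 3.6% | 13.6% |
| 60 | 30.4 | 3.2% | 12.3% |

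The figure falls if some subjects decline biopsy, is 0% if dates are spaced on purpose, and can reach 100% if early subjects are batched. It is the chance of close spacing, not of harm, and no bleeding rate is assumed.

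**The case against.** The strongest reply is that this is loose drafting rather than a design fault. Read with its opening clause, the sentence implies that staff biopsy one subject, assess that subject, and then proceed. That is a sensible intention, but the condition written down is completion of the biopsy, and a reader who follows it to the letter would comply without any assessment. If assessment was intended, one sentence makes it explicit.

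A second reply is that actual observation is unlikely to be nil. The Visit 6 list places the methacholine challenge after the biopsy, so the subject may stay on site for a supervised test. The order is not stated to be binding, and such a stay would fall far short of 24 hours. Zero is what the text guarantees, not what must happen.

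Third, there are general safeguards: the investigator can end a subject's participation (Section 11.2), the protocol chair can call an ad hoc DSMB review (Section 12.8.2.2), and serious events are reported within 24 hours (Section 12.5.1). These are real and do not require two events, but none holds the next biopsy automatically.

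Three further points stand as limits:

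- The 24-hour window is a recording definition, not a release interval, and a call at 24 hours would often miss an infection.
- The 12% to 15% rests on a scheduling assumption that the documents do not support or contradict.
- The point may already be moot. Enrollment was planned from September 2016, and this version contains a COVID-19 plan, so the first five biopsies have probably been done, although no section says so.

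**Conclusion.** The point holds, at minor severity. The stagger as written guarantees 0 hours of observation after the prior biopsy, against a stated aim of assessing what follows it and an adverse event window of 24 hours. No other section supplies a wait or a review. This conclusion rests on the text alone.

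How often it would matter depends on scheduling that the documents do not fix. Slow average accrual makes close spacing uncommon but does not exclude it. The effect is confined to participant safety in an optional, exploratory procedure with infrequent and mostly mild bleeding, and no primary or secondary analysis changes. If the first five biopsies are complete, nothing is left to correct.

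**What to change.** For any of the first five biopsies still to be done, replace the release condition in Section 5.4 with two requirements:

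1. At least 24 hours have passed since the prior participant's biopsy.
2. An adverse event check of that participant has been made and documented before the next biopsy. A phone call is enough.

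Because Day 4 is fixed, apply this through the inoculation dates: at most one of these subjects per day, with biopsy times at least 24 hours apart. If the check finds a biopsy adverse event as defined in Section 12.2.1, or cannot be made, the investigator either records a decision to go on or omits that one biopsy. State that such an omission is not a deviation.

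The cost is one amended sentence, up to four short calls, and about 4 gaps × 1 day = 4 days. This may run slightly longer, since biopsy times cannot move earlier from one day to the next. The downsides are that these five subjects cannot be batched and that an exploratory biopsy may occasionally be lost.

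Holding until the prior participant's Visit 7 is not proposed. That visit can fall on Day 8, so each gap would need 8 − 4 = 4 days, or 4 × 4 = 16 days in all, which is out of proportion to the risk.
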